5.2 Study Rationale

No curative treatment exists for mRCC, except in very few cases where a single metastasis can be surgically removed. General chemotherapy does not lead to remission and is therefore not used as regular treatment. Improved understanding of the underlying cellular mechanisms of the RCC pathogenesis has resulted in treatment evolvement from being predominantly based on cytokines (IFN- α 2a and IL-2) to the use of targeted agents, such as sunitinib. However, complete and durable unmaintained remissions are rare, and obtained survival gain is limited. In addition, these interventions are associated with severe side effects and high costs. Consequently, there is a need for development of new therapies.

So far, no signs of tumor shrinkage related to Intuvax administration has been shown in Immunicum AB's clinical pilot studies in hepatocellular carcinoma (HCC) and mRCC. However, there are indications of extended OS suggesting that the tumor growth rate might be reduced as a result of Intuvax vaccination. Furthermore, post study case reports have shown objective tumor response in three (3) out of four (4) participating patients receiving sunitinib after tumor progression including one with Central Nervous System (CNS)-metastases and one with extensive sarcomatoid tumor differentiation. These two (2) cases of objective tumor responses are unexpected since both mRCC brain metastases as well as mRCC with extensive sarcomatoid tumor differentiation are known to be highly resistant to sunitinib treatment and therefore indicate that Intuvax followed by sunitinib may have a synergistic antitumor effect [14,15].

RCC is associated with immune dysfunction including shift from type 1 to type 2 T-cell cytokine response, increased numbers of myeloid-derived suppressor cells (MDSCs) and enhanced T regulatory (Treg) cell expression. It has been shown that sunitinib improves the immune suppression seen in the microenvironment of the tumor [16,17]. In a phase I/II clinical trial a positive effect of combining autologous DC immunotherapy with sunitinib was observed in advance stage mRCC patients [18]. A phase III study in a similar patient population is ongoing for further evaluation of the concept [19].

Immunicum AB's findings presented above together with the results reported in the literature on the use of autologous DCs in combination with sunitinib encourage Immunicum AB to further investigate the possibility of exploiting Intuvax vaccination when combined with sunitinib for the treatment of mRCC patients. It is postulated that Immunicum AB's allogenic DC vaccine will stimulate a more durable clinical and immunologic response in mRCC patients when used in a combined treatment setting.

5.3 Potential Risks and Benefits

[REDACTED]

[REDACTED]	[REDACTED]
[REDACTED]	[REDACTED]
[REDACTED]	[REDACTED]
[REDACTED]	[REDACTED]
[REDACTED]	[REDACTED]
[REDACTED]	[REDACTED]

[Redacted]
	
[Redacted]

[Redacted]
	
[Redacted]

[Redacted]
	
[Redacted]

[REDACTED]	[REDACTED]
[REDACTED]	[REDACTED]
[REDACTED]	[REDACTED]

Clinical Risk/Benefit Assessment

Treatment with Intuvax immunotherapy might potentially result in prolonged survival. The risk of serious immunologic reactions is expected to be low considering data from the supporting animal studies that have been performed and the completed phase I study in mRCC patients and the ongoing phase I study in HCC patients. The risk for a serious late immune reaction with secondary organ damage (most probably in the remaining kidney) is expected to be low considering the results from the same studies.

Intuvax-induced alloimmunization does not jeopardize future RBC transfusions, since RBC lack HLA antigen expression. Moreover, there is a very low risk that mRCC patients on sunitinib treatment will require platelet-transfusions or will be transplanted with an allogeneic organ. However, if severe thrombocytopenia occurs in patients that have developed HLA-antibodies due to prior Intuvax treatment, platelet transfusion can be conducted by selecting HLA-matched platelet donors. As treatment with Intuvax, followed by sunitinib, might prolong the survival in a patient population with poor prognosis, Immunicum believe the risk benefit overview is well balanced.

6 STUDY OBJECTIVES

6.1 Primary Objectives

The primary objectives are:

- To evaluate median OS from randomization in mRCC patients overall and by subgroup, i.e. in high-risk and in intermediate-risk patients separately, receiving two (2) vaccine doses of Intuvax pre-nephrectomy, followed by sunitinib initiated five (5) to eight (8) weeks post-nephrectomy and in non-vaccinated mRCC patients receiving sunitinib initiated five (5) to eight (8) weeks post-nephrectomy
- To evaluate 18-month survival rate from randomization in mRCC patients overall and by subgroup, i.e. in high-risk and in intermediate-risk patients separately, receiving two (2) vaccine doses of Intuvax pre-nephrectomy followed by sunitinib post-nephrectomy and in non-vaccinated patients receiving sunitinib post-nephrectomy

6.2 Secondary Objectives

The secondary objectives are:

- To evaluate safety and tolerability in high- and intermediate-risk mRCC patients receiving two (2) vaccine doses of Intuvax pre-nephrectomy followed by sunitinib post-nephrectomy and in non-vaccinated patients receiving sunitinib post-nephrectomy
- To evaluate PFS according to Response Evaluation Criteria In Solid Tumors (RECIST) 1.1 criteria from Sunitinib Start Visit in intermediate- and high-risk mRCC patients after receiving two (2) vaccine doses of Intuvax pre-nephrectomy followed by sunitinib post-nephrectomy and in non-vaccinated patients receiving sunitinib post-nephrectomy*
- To evaluate response and its duration according to RECIST 1.1 criteria from Sunitinib Start Visit in intermediate- and high-risk mRCC patients receiving two (2) vaccine doses of Intuvax pre-nephrectomy followed by sunitinib post-nephrectomy and in non-vaccinated patients receiving sunitinib post-nephrectomy*
- To evaluate time to progression (TTP) from Sunitinib Start Visit in intermediate- and high-risk mRCC patients receiving two (2) vaccine doses of Intuvax pre-nephrectomy followed by sunitinib post-nephrectomy and in non-vaccinated patients receiving sunitinib post-nephrectomy*
- To evaluate the number of infiltrating CD8+ T-cells in available diagnostic pre-biopsy (sample from either primary tumor or metastasis acceptable) and in the resected primary renal tumor in intermediate- and high-risk mRCC patients receiving two (2) vaccine doses of Intuvax pre-nephrectomy and in non-vaccinated patients

*Note: For intermediate-risk patients included in the trial according to protocol versions before version Final 4.0, baseline for PFS, ORR response and its duration, and TTP is defined as the first imaging assessment after nephrectomy.

6.3 [REDACTED]

[REDACTED]

- | [REDACTED]
- | [REDACTED]
- | [REDACTED]
- | [REDACTED]
- | [REDACTED]
- | [REDACTED]
- | [REDACTED]

7 INVESTIGATIONAL PLAN

7.1 Study Design and Plan-Description

The study is an open-label, randomized, controlled, two (2) armed, multicenter, phase II study. Intermediate- and high-risk mRCC patients according to Heng criteria are eligible for participation [4]. Stratified randomization based on Heng-risk categories applies. The patients are randomized in a consecutive order to one (1) of the following two (2) treatment arms when eligibility has been confirmed;

- (i) Two (2) doses of Intuvax (10×10^6 DCs) administered intratumorally into the primary tumor 14 ± 3 days apart followed by nephrectomy at least three (3) days after the second vaccine dose.

AND

Sunitinib treatment initiated five (5) to eight (8) weeks after nephrectomy, administered dose in accordance with the SmPC/USPI.

- (ii) Sunitinib treatment initiated five (5) to eight (8) weeks after nephrectomy, administered dose in accordance with the SmPC/USPI.

The estimated number of patients to be randomized in the study is around 90. The patients will be randomized in a 2:1 (vaccine treatment arm [i]:control treatment arm [ii]) ratio. Stratification will be done at randomization for intermediate- and high-risk patients.

Patients randomized to treatment arm (i) are scheduled for 12 study visits and patients randomized to treatment arm (ii) are scheduled for 10 study visits during a study period of 78 weeks, see list below and *Figure 1*. In addition, all patients being exposed to any of the Investigational Medicinal Products (IMPs) will have a safety evaluation done for collection of SAEs up to 30 days after last dose of IMP administered in the study. The following visits apply for the two (2) patient populations:

- Screening Visit (Screening)
- Vaccination 1 Visit (Vacc1), applicable for patients randomized to treatment arm (i)
- Vaccination 2 Visit (Vacc2), applicable for patients randomized to treatment arm (i)
- Nephrectomy Visit (Nephrectomy)
- Sunitinib Start Visit (Sun-Start), five (5) to eight (8) weeks after Nephrectomy
- Sunitinib Follow-up Visits (SFU[6W] and SFU[12W]), every 6 weeks for 12 weeks or until locally CT-verified PD whichever occurs first
- Sunitinib Follow-up Visits (SFU[24W], SFU[36W], SFU[48W], and SFU[60W]), every 12 weeks until End-of study or until locally CT-verified PD whichever occurs first
- End-of-Study Visit (End-of-Study)

[figure not shown]
At the two (2) Vaccination Visits, the patients will be administered Intuvax (10×10^6 DCs) intratumorally in the viable part of their primary tumor. Vaccine from the same batch (i.e. the same donor) will be used at both occasions. The patient will stay at the clinic at least four (4) hours after vaccination. Nephrectomy is done at least 3 days after the second vaccination and maximum 63 days after Screening. Sunitinib treatment is initiated five (5) to eight (8) weeks after nephrectomy, administered dose is in accordance with the SmPC/USPI.

All patients will be encouraged to contact the clinic in between study visits if they experience adverse events (AEs) or have any concerns. If follow-up of any symptoms is needed

between the planned visits, the patient will be scheduled for a visit as soon as possible and applicable assessments will be performed.

Post-study survival data (date of death) will be collected.

Figure 1 Overall Study Design

Comment: In addition to the visits included in the figure there will be a safety evaluation performed. Any SAE occurring up to 30 days after last dose of IMP administered in the study will be collected from all patients being exposed to an IMP. Also post-study survival data (date of death) collection will continue on a yearly basis for a maximum of 5 years after collection of the last patient's 18 months survival data.

7.2 Study Procedures

7.2.1 Schedule of Study Events

The study assessments described in the sections below are presented in detail in *Section 10.2* (Efficacy assessments), *Section 10.4* (Demographic data and baseline characteristics) and *Section 10.5* (Safety assessments). Recording and reporting of AEs are described in detail in *Section 11* (Adverse Events).

The timing of all study events is presented in *Section 7.2.1.1* to *Section 7.2.1.9* and in *Table 2* (study flow chart), and *Table 3* (details on assessments in connection with vaccination for all patients randomized to Intuvax).

7.2.1.1 Screening Visit

This visit is applicable for all patients.

ACTIVITIES AND ASSESSMENTS:

- Informed Consent, *Section 13.1.3*
- Demography, *Section 10.4.1*
- Medical and Surgical history, *Section 10.4.2*
- CT Scan to be done within 3 weeks from Screening Visit unless a CT scan has been performed in clinical routine within 6 weeks prior to Screening Visit, *Section 10.4.3*
- Brain imaging (preferably by contrast-enhanced) Magnetic Resonance Imaging (MRI) or CT to be done within 3 weeks from Screening Visit unless a CT scan has been performed in clinical routine within 6 weeks prior to Screening Visit, *Section 10.4.3*
- Prior Medication, *Section 10.4.4*
- Physical Examination, *Section 10.5.3*

- Vital Signs, *Section 10.5.4*
- ECG, *Section 10.4.5*
- Laboratory Safety Blood Assessments: Hematology, Clinical Chemistry including Glomerular Filtration Rate (GFR) based on Creatinine (Creat), Glucose (Gluc), Thyroid stimulating hormone (TSH), Thyroxine (free T4), and Prothrombin Time - International Normalized Ratio (PT-INR), Activated Partial Thromboplastin Time (APTT), and Pregnancy *Section 10.5.5*
- Laboratory Safety Urine Assessments, *Section 10.5.5*
- Additional Laboratory Blood Assessments: Serology (HIV, HBV, and HCV), *Section 10.4.6*, High resolution tissue typing of Human Leukocyte Antigens (HLA), *Section 10.4.7*
- ECOG score, *Section 10.2.3.1* and Karnofsky performance status, *Section 3.2*
- █████ *Section 10.2.3.2*
- Inclusion/Exclusion Criteria, *Section 8.2* and *Section 8.3*. To be checked when the results from all assessments made at Screening are available.
- Randomization, *Section 9.2*. To be done when eligibility has been confirmed.
- Confirmatory diagnostic biopsy in accordance with local routines prior to Vacc1 Visit, if required by local regulations and laws, *Section 9.2*.
- AEs, *Section 11.2*

A telephone contact will be made with the patient once randomization has been done in order to inform about which treatment the patient was allocated to and for scheduling the next study visit and a confirmatory biopsy if applicable.

Extra consent for vaccination for patients randomized to the vaccine arm, to be taken after randomization if required by local regulations.

7.2.1.2 Vacc1 Visit (if applicable)

This visit is applicable only for patients randomized to Intuvax followed by sunitinib.

TIME WINDOW:

Vacc1 Visit to be done within 28 days after Screening

ACTIVITIES AND ASSESSMENTS:

Day before vaccination (optional):

The following assessments may be done the day before vaccination for logistical reasons:

- Laboratory Safety Blood Assessments: Hematology, Clinical Chemistry, PT-INR, and APTT, *Section 10.5.5*
- Pregnancy (either blood or urine), *Section 10.5.5*
- Laboratory Safety Urine Assessments, *Section 10.5.5*
- Physical Examination, *Section 10.5.3*
- ECOG performance status, *Section 10.2.3.1*
- AEs, *Section 11.2*

Day of vaccination (Pre-Vaccination):

NB: Absolute fasting for four (4) h prior to Intuvax administration applies.

- Concomitant Medication, *Section 10.4.4*
- Physical Examination unless done the day before, *Section 10.5.3*
- Vital Signs, *Section 10.5.4*
- Laboratory Safety Blood Assessments: Hematology, Clinical Chemistry, PT-INR, and APTT unless done the day before, *Section 10.5.5*
- Pregnancy (either blood or urine test) unless done the day before, *Section 10.5.5*
- Laboratory Safety Urine Assessments unless done the day before, *Section 10.5.5*
- Auto- and alloimmunization (baseline), *Section 10.5.6.1* and *Section 10.5.6.2*
- ECOG performance status unless done the day before, *Section 10.2.3.1*
- AEs, *Section 11.2*

Day of vaccination (Vaccination)

- Injection of Intuvax into the viable part of the renal tumor using CT or Ultrasound monitoring for confirmation of administration location, *Section 9.1.5*

Day of vaccination (Post-Vaccination)

- Vital Signs, *Section 10.5.4*
- AEs, *Section 11.2*
- Concomitant Medication, *Section 10.4.4*

7.2.1.3 Vacc2 Visit (If applicable)

This visit is applicable only for patients randomized to Intuvax followed by sunitinib.

TIME WINDOW:

14 days (± 3 days) after Vacc1 Visit

ACTIVITIES AND ASSESSMENTS

Exactly the same activities and assessments will be done at this visit as was done on Vacc1 Visit except for auto- and alloimmunization, *Section 7.2.1.2*.

7.2.1.4 Nephrectomy Visit

This visit is applicable for all patients.

TIME WINDOWS:

At least 3 days after Vacc2 Visit and within 63 days from Screening Visit for patients randomized to Intuvax followed by sunitinib.

Within 63 days from Screening Visit for patients randomized to sunitinib only.

ACTIVITIES AND ASSESSMENTS:

Prior to Nephrectomy (may be done the day before vaccination for logistical reasons)

- Concomitant Medication, *Section 10.4.4*
- Laboratory Safety Blood Assessments: All patients: Hematology and Clinical Chemistry, for patients on anticoagulants: also PT-INR, and APTT, *Section 10.5.5*

- Laboratory Safety Urine Assessments, *Section 10.5.5*
- █████, *Section 10.2.3.2*
- AEs, *Section 11.2*

Nephrectomy and post Nephrectomy assessments

- Nephrectomy, *Section 9.1.1*
- Biopsies for central assessments of infiltrating CD8+ T-cells and immunohistology, *Section 10.2.2.4* and *Section 10.2.3.3*.
- AEs, *Section 11.2*
- Confirmation of mRCC diagnosis, *Section 10.4.2*

7.2.1.5 Sun-Start Visit

This visit is applicable for all patients.

TIME WINDOW:

Five (5) to eight (8) weeks after Nephrectomy Visit

NB: The CT scan does not have to be done the very same day as the study visit. However, it has to be done within the above specified time window.

The laboratory safety blood and urine assessments do not have to be done the very same day as the study visit. However, it has to be done a maximum of 3 days prior to the visit.

ACTIVITIES AND ASSESSMENTS:

- CT Scan, *Section 10.4.3* including specification of target lesions *Section 10.2.2.2*
- Concomitant Medication, *Section 10.4.4*
- Physical Examination, *Section 10.5.3*
- Vital Signs, *Section 10.5.4*
- Laboratory Safety Blood Assessments: Hematology and Clinical Chemistry including GFR based on Creat, Gluc, TSH, and Thyroxine [free T4], *Section 10.5.5*
- Laboratory Safety Urine Assessments, *Section 10.5.5*
- Auto- and alloimmunization (only for patients treated with Intuvax), *Section 10.5.6.1* and *Section 10.5.6.2*
- ECOG performance status, *Section 10.2.3.1*
- █████ *Section 10.2.3.2*
- Start of sunitinib treatment. Dispense of sunitinib, *Section 9.1.4*
- AEs, *Section 11.2*

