3.2 Definition of Terms

NB: Detailed definitions of terms from the updated guideline Response Evaluation Criteria In Solid Tumors (RECIST v1.1) [1] are included in *Section 10.2.2.2* and detailed definitions for Dose Limiting Toxicity (DLT) based on Common Terminology Criteria for Adverse Events (CTCAE) grading [2] for specific AEs are presented in *Section 11.5*.

Baseline	
The date of randomization is defined as baseline for OS and 18-month survival rate.
 
The centrally assessed CT performed at the Sunitinib Start Visit is defined as CT baseline for evaluation of PFS, response rate and time to progression (TTP) after start of sunitinib in intermediate- and high-risk patients, Section 10.2.2.1, Section 10.2.2.2, and Section 10.2.2.3. Note: For intermediate-risk patients included in the trial according to protocol versions before version Final 4.0, baseline for PFS, ORR and duration of response, and TTP is defined as the first imaging assessment after nephrectomy.
 
The Screening Visit is defined as baseline for all other assessments than those listed above.

Competent Authority (CA)	A government body or government appointed body that has legal authority to approve or disapprove clinical studies
Eastern Cooperative Oncology Group (ECOG) criteria (also referred to as WHO or Zubrod) [3]	
0 Fully active, able to carry on all pre-disease performance without restriction
 
1 Restricted in physically strenuous activity but ambulatory and able to carry out work of a light or sedentary nature, e.g., light house work, office work
 
2 Ambulatory and capable of all self-care but unable to carry out any work activities. Up and about more than 50% of waking hours
 
3 Capable of only limited self-care, confined to bed or chair more than 50% of waking hours
 
4 Completely disabled. Cannot carry on any self-care. Totally confined to bed or chair
 
5 Dead

High-risk mRCC patient according to Heng criteria [4]	
Patients fulfilling three (3) to six (6) of the following prognostic factors:
 
 • Hemoglobin (Hb) less than the lower limit of normal (LLN) • Corrected Calcium (Ca) greater than upper limit of normal (ULN) • Karnofsky performance status less than 80% • Time for diagnosis to treatment less than one (1) year • Neutrophils greater than ULN • Platelets greater than ULN

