AEs	X	X ^c	X ^c	X	X	X	X	X ^k	X ^v	X
Diagnosis Confirmation ^f				X						

a Assessment to be completed before nephrectomy and may be done the day before nephrectomy for logistical reasons

Locally analyzed Creatinine for patients included in the study before 28 August 2017 (if performed as part of clinical routine) to be recorded in eCRF

b Height only at Screening. Weight at all visits except for Vacc1 and Vacc2 Visits.

c See specific flow chart, *Table 3*, for detailed instructions on pre- and post-vaccination assessments.

d Physical examination, ECOG performance, and samples for safety lab and urinalyses may be taken the day before vaccination for logistical reasons

Locally analyzed results for Hb, WBC, platelets, PT-INR, and APTT need to be available before vaccination

Locally analyzed results for Hb, WBC, and clinical chemistry might need to be available prior to nephrectomy

- Analysis of coagulation status at Nephrectomy is not necessary provided the patient is not on anticoagulant treatment. For patients on anticoagulants local sampling practice applies.
- e Pregnancy test in blood at Screening, and in either blood or urine at Vacc1 and Vacc2 Visits. The pregnancy test result is needed prior to each vaccination.
 - f Samples for auto- and alloimmunization analyses will be collected prior to vaccination at Vacc1 Visit. Sampling at Sun-Start Visit only applicable for patients randomized to Intuvax.
 - g To be done when the results from all assessments made are available. Telephone contact with patient to inform about treatment and timing of next study visit.
 - h The prescribed dose to be in accordance with the SmPC/USPI including any dose adjustments.
 - i Return of sunitinib not applicable at Sun-Start Visit and Distribution not applicable at End-of-Study Visit. Standard of Care applies after End-of-Study.
 - j Start of sunitinib administration will be dependent on wound healing. The time window for initiation is five (5) to eight (8) weeks after Nephrectomy.
 - k Post-study collection of survival data.
 - l If CT cannot be used for some reason, MRI is acceptable. The same modality has to be used at all visits.

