 - m CT scan to be done within 3 weeks before Screening unless a CT scan has been done in clinical routine within 6 weeks before Screening. Brain imaging (preferably by contrast-enhanced) MRI or CT to be done within 3 weeks before Screening Visit unless a CT scan has been performed in clinical routine within 6 weeks prior to Screening Visit
 - n To be done if Extra Visit is scheduled after Sun-Start Visit
 - o If SFU[60W] is scheduled ≥ 76 weeks since Screening this visit should be considered the End-of-Study Visit
 - p Confirmatory diagnostic biopsy in accordance with local routines prior to Vacc1 Visit, if required by local regulations and laws
 - q Absolute fasting for four (4) h prior to Intuvax administration applies
 - r Routine histology/Primary diagnosis is assessed locally
 - s Extra consent for vaccination for patients randomized to the vaccine arm, to be taken after randomization if required by local regulations
 - t The CT scan does not have to be done the very same day as the corresponding study visit. However, each CT scan has to be done within the specified time window for the corresponding visit
 - u The laboratory safety blood and urine assessments do not have to be done the very same day as the study visit. However, it has to be done within 3 days prior to the visit.
 - v SAEs only to be recorded and reported, see *Section 11.2*

Table 3 Detailed Instructions on Assessments in Connection with Vaccination

Assessment	Pre-vaccination	Vaccination	Post-vaccination					
	> 2 h	0 h	15 min (±5 min)	30 min (±10 min)	60 min (±10 min)	2 h (±10 min)	3 h (±10 min)	4 h (±20 min)
Intuvax injection		X						
BP	X		X	X	X	X	X	X
HR	X		X	X	X	X	X	X
Body temperature	X			X	X	X	X	X
AEs	X		X	X	X	X	X	X

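### The baseline CT for response, PFS and TTP may be taken up to 21 days after the first sunitinib dose, and the SAP has no rule for such scans

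*Protocol*

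**What the plan says.** Protocol section 3.2 fixes the reference scan: "The centrally assessed CT performed at the Sunitinib Start Visit is defined as CT baseline" for PFS, response rate and TTP. SAP section 6.3.1 repeats this. Intermediate-risk patients enrolled before protocol version 4.0 have a separate baseline, the first imaging after nephrectomy.

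Protocol section 7.2.1.5 gives the visit window as "Five (5) to eight (8) weeks after Nephrectomy Visit". On the scan it says: "The CT scan does not have to be done the very same day as the study visit". The one condition follows: "However, it has to be done within the above specified time window". Footnote t of the flow chart (section 7.2.2) has the same rule: "each CT scan has to be done within the specified time window for the corresponding visit".

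Dosing belongs to the same visit, whose activities include: "Start of sunitinib treatment. Dispense of sunitinib". Footnote j says of sunitinib: "The time window for initiation is five (5) to eight (8) weeks after Nephrectomy". Scan and first dose thus share one window, and no order between them is stated. The laboratory samples at this visit are treated differently. They may also be taken on another day, but "it has to be done a maximum of 3 days prior to the visit".

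The time origin is not the scan. Protocol section 10.2.2.1 counts PFS from the Sunitinib Start Visit, and SAP section 6.3.6 counts it from the date sunitinib started.

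**The concern.** A baseline scan should show the disease before the treatment whose effect is being measured. Here a patient can start sunitinib early in the window and be scanned late in it. The baseline is then an on-treatment scan, although the endpoints are described as running from the start of sunitinib.

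Three things follow. Partial response is measured from a sum that may already have moved. The starting point for judging progression changes too. PFS and TTP time can begin before the scan against which progression is assessed. Pre-dose and on-dose baselines would then be mixed within one endpoint, with nothing in the SAP to identify the on-dose ones.

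**Working it through.** The plan states no figure on this point, so there is none to reproduce. The check is window arithmetic, followed by the protocol's own response rules applied to illustrative sums.

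**Inputs**

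- Window for both CT and first dose: 5 to 8 weeks after nephrectomy, i.e. day 35 to day 56 (Protocol 7.2.1.5; 7.2.2, footnotes j and t).
- First follow-up scan, SFU[6W]: 42 ± 7 days after Sun-Start (Protocol 7.2.1.6).
- Standard sunitinib cycle: 4 weeks on, 2 weeks off (Protocol 9.1.5).
- Partial response (PR): a fall of at least 30% from the baseline sum (Protocol 10.2.2.2, Table 4).
- Progression (PD) on target lesions: a rise of at least 20% and at least 5 mm from the smallest sum on study, which may be the baseline sum (same table).
- Size of any change before a late baseline: not in the documents, so assumed and shown as a range.

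**Timing**

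- Longest permitted lag of CT behind first dose: 56 − 35 = 21 days, or 21/28 = 75% of the on-drug days of a first cycle.
- The same wording also permits a CT up to 21 days before the first dose.
- Baseline CT to first follow-up CT at that lag: (42 − 7) − 21 = 14 days up to (42 + 7) − 21 = 28 days. With a same-day baseline it is 35 to 49 days.

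**Response**

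Take a pre-dose sum of 100 mm and a fraction s of shrinkage before the baseline scan. The recorded baseline is 100(1 − s), and PR is reached at 70(1− s). The true fall needed, in per cent, is 100 − 70(1 − s). A true 30% fall is recorded as 70/[100(1 − s)] − 1.

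| Assumed early shrinkage | Recorded baseline (mm) | PR reached at (mm) | True fall needed | True −30% recorded as |
|---|---|---|---|---|
| 0% | 100 | 70.0 | 30.0% | −30.0% |
| 5% | 95 | 66.5 | 33.5% | −26.3% |
| 10% | 90 | 63.0 | 37.0% | −22.2% |
| 20% | 80 | 56.0 | 44.0% | −12.5% |

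For example, a best sum of 68 mm is 68/100 − 1 = −32% from the pre-dose scan, a PR. From a 90 mm late baseline it is 68/90 − 1 = −24.4%, which is stable disease.

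**Progression**

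Illustrative sums in mm; the late baseline is the week-3 scan.

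| Pre-dose, week 3, week 6, week 12 | PD with pre-dose baseline | PD with late baseline |
|---|---|---|
| 100, 85, 75, 91 | Week 12 (91/75 = +21.3%) | Week 12 (same nadir of 75) |
| 100, 85, 103, 110 | None (+3%, +10%) | Week 6 (103/85 = +21.2%) |
| 100, 110, 125, 133 | Week 6 (+25%) | Week 12 (125/110 = +13.6%; 133/110 = +20.9%) |

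In the first row the later nadir governs and nothing changes. In the second the lower baseline sum makes PD easier to meet. In the third early growth is absorbed into baseline and PD is delayed. A lesion that first appears between the first dose and a late scan would likewise be recorded as baseline disease, not as a new lesion.

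**The case against.** The best reply is that the gap is one of wording. Section 3.2 speaks of the CT performed at the Sunitinib Start Visit, and section 7.2.1.5 lists the CT first and the start of sunitinib near the end, which suggests scan before dose. But the list is not stated as a sequence, and the same section expressly frees the CT from the visit day. Section 10.4.3 also refers to a separate imaging protocol and a further study-specific instruction, which may settle the order. Neither can be seen, so the gap is shown for the protocol and SAP only.

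Several limits stand in full. The 21 days needs the first dose on the first permitted day and the scan on the last; the 14 days also needs the earliest permitted follow-up scan. Neither has a known frequency. OS and 18-month survival run from randomization and are untouched. The trial is exploratory and its size is not based on a power calculation.

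The timetable also limits a change of protocol text. The SAP is based on version 9.0 of 12 February 2019, and the last visit is planned for the third quarter of 2019. Counting 76 weeks back from the end of September 2019 gives a last screening around mid-April 2018. Adding 63 + 56 = 119 days puts the last Sun-Start window around mid-August 2018. On the planned timeline the scans had been taken, which leaves the SAP rule as the useful action.

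A reader might infer that early shrinkage is lost from the progression reference as well. The protocol does not support that: PD is judged against the smallest sum on study, so a shrunken baseline carries the shrinkage into the reference. A reader might also infer a bias between arms. The CT rule is the same in both, and section 10.4.3 keeps the central assessor unaware of treatment assignment. The study is open-label, but nothing in the documents shows that scan timing differs by arm.

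**Conclusion.** The concern holds in a limited form. The text permits a baseline CT up to 21 days after the first sunitinib dose, and the SAP does not say how such a scan is handled.

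For response, the effect is downward wherever the tumour has shrunk before the scan. The true fall needed for PR rises from 30% to 33.5, 37 or 44% under assumed early shrinkage of 5, 10 or 20%. Those percentages are assumptions; the documents give no estimate. For PD the direction is not fixed: it can come earlier, later or not move. DCR is affected only through PD, because a PR read as stable disease still counts as disease control. PFS and TTP time zero can precede the baseline scan by up to the same 21 days.

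This is a modest point on secondary endpoints. Its practical weight depends on how many patients had a post-dose baseline, which the documents do not tell. It does not apply in the same way to intermediate-risk patients enrolled before version 4.0, whose baseline is defined separately.

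**What to change.** **Protocol.** Reconcile section 3.2, section 7.2.1.5, footnote t of the flow chart and section 10.4.3 so that, for any scan still to be taken, the baseline CT is on or before the first sunitinib dose. This concerns the date of the scan only. It costs a phrase and a little scheduling freedom.

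**SAP section 6.3.6.** Add a rule that flags every patient whose baseline CT is dated after the first dose, and report the number flagged by arm. Repeat ORR/DCR, PFS and TTP without the flagged patients as a sensitivity analysis, leaving the main FAS analysis as it is. State how intermediate-risk patients enrolled before version 4.0 are treated, since some started sunitinib late or never. An earlier post-nephrectomy CT cannot be relied on as a substitute, because the flow chart schedules none between Screening and Sun-Start.

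The dates needed are available: section 10.4.3 collects CT dates, and the SAP already uses the sunitinib start date for PFS. The cost is one extra run on fewer patients. Because it excludes patients on a post-randomization fact, it should be read as supportive only.
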